#### 4.2 Stereotactic Body Radiation Therapy (SBRT)

> Radiation therapy has a long and established history in the field of oncology[18]. Recently, technological advances have allowed radiation oncologists to effectively treat tumors anywhere in the body using SBRT[19]. This ability to deliver high tumoricidal doses while limiting dose to surrounding normal structures has been a major advance and fundamental shift in the field of radiation oncology. The term stereotactic radiation or stereotaxy refers to the use of a referenced three-dimensional coordinate system to locate targets inside the body and deliver highly focused beams of radiation to that site with millimeter accuracy. Stereotactic delivery of radiation is usually termed stereotactic body radiation therapy (SBRT) for extracranial tumors, and referred to as Stereotactic Radiosurgery (SRS) for intracranial tumors. Because of the accuracy and ability to precisely modify the radiation dose distribution to minimize radiation to normal tissue, stereotactic radiation allows for "hypofractionation" or delivery of very high doses of radiation during each fraction of treatment. In the United States, clinical stereotactic radiation courses are currently completed in 1 to 5 fractions total. This is a dramatic shortening of total treatment time compared to conventionally fractionated radiation which can range from between 2-8 weeks or 10-40 fractions to complete. Clinically, stereotactic radiation achieves excellent local control rates, for example SRS for AVMs[20], trigeminal neuralgia[21], pituitary adenoma[22], brain metastases[23]. SBRT for early stage lung cancer has local control rates rivaling those of surgery[24].

> SBRT is also being increasingly used as an effective local therapy for metastatic lesions or in patients with oligometastatic disease. Local control rates greater than 75% have been reported for metastatic tumors of the lung, liver, and spine, which is significantly higher than standard conventional moderate dose radiation[25-27]. Given these response rates, SBRT is being used in place of surgery for oligometastatic disease to target pulmonary metastasis, especially in patients who are not optimal surgical candidates. A number of institutions have reported favorable outcomes using either single or multi-fraction SBRT for oligometastatic sites within the lung. For example, a 90% control rate at 9 months was reported with SBRT was prescribed to 26 Gy in a single fraction[28]. Hof et al, reported a 63% progression free survival at 3 years when SBRT was prescribed to 12-30Gy[29]. Le et al, treated early stage and metastatic lung tumors with SBRT using doses of 15-30 Gy and report a local control of 91% for doses greater than 20 Gy and 54% for doses less than 20 Gy[26]. However, toxicity was rare when doses of less than 25 Gy were given [26]. Thus a dose of 9.5 Gy x 3 will allow for safe targeting of pulmonary metastases. Radiosensitizing effects of checkpoint blockade may result in synergistic effects and may improve the local control rates radiation while providing acceptable toxicity. There have been reports of high grade pneumonitis in patients receiving anti-PD-1/PD-L1 checkpoint blockade, although there has been no definitive evidence of supra-additive toxicity when radiation is combined with CBI[30, 31].

> Regarding liver metastases, systemic chemotherapy or molecular-targeted agents rarely achieve long term control. On the other hand, surgical removal of colorectal liver metastases has resulted in reported 5-year survival rates approaching 50%, demonstrating that local therapy has a potential curative role in patients with oligometastatic disease[17, 25, 32]. In inoperable patients, the benefit of local therapy is

less clear, however long-term survival has been reported after the resection of liver metastases from sarcoma, breast cancer, and other histologies [33]. Classically the dose limiting toxicity with radiation therapy to the liver has been radiation-induced liver disease (RILD). However, with the technological advances in radiation therapy and image guidance SBRT can now be delivered safely resulting in high tumor doses to portions of the liver while sparing other portions of the liver. For example, no cases of RILD after radiation for colorectal liver metastases were seen when the mean liver dose was <31 Gy at the University of Michigan[34]. A phase I dose-escalation trial of single fraction treatment for liver metastases reported even high doses up to 30Gy in 1 fraction with no dose-limiting toxicity and a 2 year actuarial survival rate of 50% at a medial followup of 17 months[35].

In summary, SBRT has been well tolerated and efficacious with minimal toxicity in national and international trials. This significant advancement in radiation technology and capability calls for a re-evaluation of the effects of focused radiation on the immune system and in combination with immunotherapy. Based on data above, in this study we will evaluate whether CBI plus 28.5Gy of SBRT (9.5Gy x 3 fractions) improves objective response rates and local as well as distant control.

#### 4.3 Checkpoint Blockade Immunotherapy

Recently, there have been several significant and critical advancements in the immunotherapy field[37, 38] including adoptive T-cell transfer, dendritic cell vaccines, peptide vaccines, oncolytic viruses, cytokine therapy, agonist monoclonal antibodies, and small molecules. Of these new advancements, checkpoint blockade Immunotherapy (CBI) is perhaps one of the most exciting in recent years. The significant interest in checkpoint blockade immunotherapy (CBI) stems from the dramatic and durable responses observed in a subset of patients with metastatic disease who have been heavily pre-treated. At its core, CBI functions to inhibit negative regulators of immune responses, or in other words removing the brakes on the immune system. For decades immunotherapy approaches have focused on attempting to positively stimulate the immune responses without necessarily addressing the powerful negative regulatory systems that are in place which dampen or prevent excessive immune responses. It is now understood that disabling these negative regulators or checkpoints can result in robust and clinically efficacious immune responses which in some cases can control widely metastatic disease. CTLA-4 (Cytotoxic lymphocyte antigen 4) is a receptor present on the surface of T-cells which binds the co-stimulatory molecules B7-1 and B7-2 on APCs with a much higher affinity than CD28. Instead of transmitting a positive co-stimulatory signal to the T-cell, ligation of CTLA-4 transmits a powerful inhibitory signal to T cells which can block T-cell activation. Indeed, CTLA-4 is one of the most powerful negative regulatory molecules on the cell surface of T-cells[36]. Similarly, Programmed death receptor 1 (PD-1) is a receptor on T-cells which binds PD-L1 or PD-L2 and recruits SHP phosphatases to impose a powerful inhibitory signal on T-cell activation and proliferation. Inhibiting the CTLA-4 and PD-1 pathways is now FDA approved for metastatic melanoma, NSCLC cell lung cancer and Kidney Cancer.

In 2011 the FDA granted approval to the anti-CTLA-4 drug ipilimumab (Yervoy, Bristol-Myers Squibb) for the treatment of unresectable or metastatic melanoma. In Sept 2014 the FDA granted approval to the anti-PD-1 drug pembrolizumab (Keytruda, Merck Sharp & Dohme Corp.) for the treatment of patients with unresectable or metastatic melanoma.

In Dec 2014 the FDA granted accelerated approval for the anti-PD-1 drug nivolumab (Opdivo, Bristol-Myers Squibb) for patients with progressive unresectable or metastatic melanoma after treatment with ipilimumab or BRAF inhibitor. Nivolumab received FDA approval on March 4th 2015 for treatment of advanced squamous NSCLC that has progressed after treatment with platinum-based chemotherapy. In the phase II clinical trial CheckMate-063, tumors shrank in 15% of patients who took Opdivo, and 26% had stable disease. Additionally the phase III CheckMate-017 trial in which NSCLC patients received either docetaxel chemotherapy or Opdivo was stopped early after it became evident that nivolumab outperformed docetaxel. In Sept 2015 the FDA granted accelerated approval to nivolumab in combination with ipilimumab for the treatment of patients with BRAF V600 wild-type, unresectable or metastatic melanoma. Along the same lines, the anti-PD-1 drug Keytruda

(Pembrolizumab) received FDA approval on Oct 2nd, 2015 for advanced (metastatic) non-small cell lung cancer (NSCLC) whose disease has progressed after other treatments and with tumors that express a protein called PD-L1. In the KEYNOTE-001 trial Keytruda resulted in an overall response rate of 41% (n=25/61) in patients who had PD-L1 positive tumors (Tumor proportion score ≥ 50%). In Nov 2015 the FDA approved Nivolumab to treat patients with advanced (metastatic) renal cell carcinoma. Additionally CBI has demonstrated clinical activity in a variety of tumor types including bladder cancer, Hodgkin's lymphoma, and prostate cancer among many others [4-6, 30, 37-42]. The body of clinical data evaluating the activity of CBI is established and remarkable[39-46] with additional FDA approved indications for different disease sites anticipated.

Immunotherapies and CBI can have unique profile of side effect termed termed immune-related adverse events (irAEs). Examples of irAE include dermatologic (rash), gastrointestinal (colitis), hepatic (hepatitis), endocrine (hypophysitis), pulmonary (pneumonitis) and are thought to relate to general increased activity of the immune system and inflammation. CBI has been studied in Phase III clinical trials with large numbers of patients evaluated and the general frequencies of irAE have been reported. These reported frequencies serve as reference values for estimating any increased toxicity with combinatorial therapies.

#### 4.4 Rationale for SBRT combined with CBI

There is now an established body of pre-clinical literature demonstrating that radiation can modify anti-tumor immune responses. Radiation has been demonstrated to cause upregulation of Major Histocompatibility Complex (MHC) and increase presentation of antigens on surface of tumor cells [43-48]. The DNA damage and reactive oxygen species induced by radiation have been shown to result in inflammatory tumor cell death and release of damage associated molecular patterns (DAMPs), including high mobility group box chromosomal protein 1 (HMGB1), which can activate antigen presenting cells[49-51]. Radiation induced activation of antigen presenting cells has also been demonstrated in animal models to enhance tumor antigen cross-presentation in the draining lymph node and result in activation and proliferation of tumor specific cytotoxic T-cells[47, 52-57]. Radiation has also been shown to influence expression of cytokines and chemokines, such as IL-1, IL-2, L-6, TNF-alpha, TGF-beta, CXCL-16, as well as Type I and Type II Interferons which may play a critical role in modulating immune responses[58-65]. Undoubtedly due to the culmination of these effects, multiple groups have demonstrated that radiation can cause tumor cells to become more susceptible to immune mediated attack[44, 45, 66]. Indeed some authors have suggested that the therapeutic effects of radiation alone may depend on the status of the host immune system and anti-tumor immune responses in the radiation field[54, 63, 67-69]. Given these effects using radiation alone there has been a significant effort to combine radiation with various immunotherapies with sometimes striking results within the radiation field (radiosensitizing immunotherapy), as well as distantly outside the radiation field (abscopal responses)[44, 47, 53, 65, 66, 69-78]. A number of excellent

reviews have also highlighted the potential benefits and ongoing clinical trials of radiation combined with immunotherapy[61, 79-83].

Along these lines, recent evidence has demonstrated that focused radiation can in fact stimulate an anti-tumor immune response outside of the radiation field, termed the abscopal effect. This phenomenon was originally coined by Dr. R.H. Mole in 1953 as an effect of radiation away from the primary target, or in other words, an action at a distance (49). Work by Silvia Formenti and colleagues from New York University has further characterized the abscopal effect (50) (51). Demaria et al. found that growth of a non-irradiated mammary carcinoma was impaired with the use of Flt3-ligand and radiation to a contralateral tumor (50). The authors also provided evidence that this effect was T-cell dependent as it was not observed in T-cell deficient hosts. Given that radiation is capable of inducing inflammation, apoptosis, cell death, and release of tumor antigens (53), this would create an ideal local environment for induction of a potent immune response (50) (54) (55) (56). Thus the preponderance of pre-clinical data would suggest that adding SBRT to CBI has the potential to enhance systemic anti-tumor immune responses which could help to control systemic metastatic disease and improve objective response rates. Indeed, a number of ongoing clinical trials are evaluating radiation therapy combined with CBI.

On the basis of this preclinical and clinical evidence, we propose a phase II study of CBI combined with SBRT in patients with metastatic disease. With published data establishing the relative safety of multi-fraction SBRT to the brain, lungs, liver, prostate, and pancreas, we have decided to proceed with 28.5 Gy of SBRT (9.5Gy x3 fractions) concurrently with CBI. However, the use of a three fractions concurrent with CBI is not of proven benefit. This investigation aims to confirm the safety and efficacy for SBRT used concurrently with a CBI in the setting of metastatic disease. The dose selected has been carefully chosen with the belief that it is safe and effective based on prior experience with SBRT. All patients will be treated with three fractions, targeted to the lesion concurrently with CBI.

Patient's with metastatic disease have a poor prognosis. Current treatment modalities are generally palliative and patients are rarely cured, thus additional treatment modalities are certainly needed. This proposed study represents a logical extension of the current understanding of immunotherapy and radiation therapy and potential for synergy between these two modalities. This study will refine the current understanding of radiation tolerance for normal tissues in 3 fractions, thereby making it possible to treat future patients more safely and aggressively. Additionally, this study could identify a new indication for SBRT in specifically for enhancing the systemic effects of immunotherapy. Finally, this study has the potential to translate into improved local as well as distant control ultimately improved overall survival.

#### 5. PARTICIPANT SELECTION AND ENROLLEMENT CRITERION

#### 5.1 Inclusion Criteria

- 5.1.1 The PI or Co-Investigator Radiation Oncologist states that one of the lesions can be treated with SBRT.
- 5.1.2 Patient must have at least 1 site of measurable disease by Response Evaluation Criteria in Solid Tumors (RECIST) 1.1 criteria on computed tomography (CT) or Magnetic resonance imaging (MRI) which will not be irradiated.
- 5.1.3 Histological confirmation of malignancy (primary or metastatic tumor).
- 5.1.4 Patient may have any prior therapy allowed aside from having had prior radiotherapy to the treatment site (see exclusion criteria 5.2.3).
- 5.1.5 Patient must be  $\geq 3$  years of age.
- 5.1.6 Lansky scale score of  $\geq$ 70 (ages  $\geq$  3 or < 16 years) OR Karnofsky scale score of  $\geq$ 70 (ages  $\geq$  16 or < 18 years) OR ECOG performance status  $\leq$  2 (18 years or older).
- 5.1.7 Patient's screening laboratory values must meet the following criteria:

Leukocytes $\geq 2,000/\mu L$ Absolute Neutrophil Count $\geq 1,000/\mu L$ Platelets $\geq 50,000/\mu L$ 

Total bilirubin \leq 2x institutional upper limit of normal
AST(SGOT)/ALT(SGPT) <2.5 X institutional upper limit of

normal

Serum creatinine  $\leq 1.5x$  ULN or creatinine clearance  $(CrCl) \geq 40$  mL/min (using the

Cockcroft-Gault formula):

- (1) Female CrCl = (140 age in years) x weight in kg x 0.85 /72 x serum creatinine in mg/dL
- (2) Male CrCl = (140 age in years) x weight in kg x 1.00/72 x serum creatinine in mg/dL

Pulse Oximetry

≥92% on Room Air at Rest

- 5.1.8 Patient or parent/legal guardian must have the ability to understand and the willingness to sign a written informed consent document.
- 5.1.9 For Patients <18 years of age, enrollment on trial and potential for use of CBI or CBI combined with SBRT must be agreed upon by consensus opinion of a multidisciplinary pediatric tumor board.

#### 5.2 Exclusion Criteria

5.2.1 Patient has had chemotherapy or radiotherapy within 4 weeks prior to entering the study or those who have not recovered from adverse events due to agents

administered more than 4 weeks earlier.

- 5.2.2 Patient receiving any investigational or experimental agents other than immunotherapy.
- 5.2.3 Patient who has had any prior radiotherapy to the treatment site(s).
- 5.2.4 Patient is a pregnant woman (pregnant women are excluded from this study because radiation treatment has known potential for teratogenic or abortifacient effects).
- 5.2.5 Patient refuses to sign informed consent.

#### 6. TREATMENT PLAN

#### **6.1 Diagnostic Procedures**

A CT scan or MRI will be performed for tumor localization using rigid immobilization appropriate for stereotactic treatment. A separate PET-CT may be performed (optional) for diagnostic purposes and can be used for treatment planning with fusion – the identical study would be performed if the patient were having standard conventional dose radiation.

#### **6.2** Therapeutic Procedures

Patients will be pre-screened for eligibility and should be enrolled and randomized prior to starting immunotherapy. However, patients who have started immunotherapy up to 5 days prior to enrollment will be still be eligible for screening, randomization, and enrollment.

Upon confirmation of eligibility and enrollment in the study, the following will be completed:

- 1) Demographics review, medical history and clinical exam
- 2) Review of concurrent medications
- 3) Vital signs, height and weight
- 4) Laboratory Bloodwork including: CBC, BMP, LFT.
- 5) Plasma and Peripheral blood mononuclear cells will be collected and subsequently frozen for immune monitoring assays.
- 6) Tumor measurements (Recist 1.1) within 4 weeks prior to start of CBI

Upon randomization into the SBRT arm of the protocol, patients will be seen by at least one of the Co-Investigator Radiation Oncologists. CT simulation will be performed with fabrication of a radiation therapy immobilization device (such as a Vac-Lok) which will be custom made for each patient. The treating radiation

oncologist will identify the location of the tumor. Gross tumor volume (GTV) delineation will be performed on sequential axial computed tomography images. An SBRT treatment plan will be developed based on tumor size and location. The dose will be prescribed to the minimal isodose line that completely covers the GTV plus a 5 mm margin. Adjacent normal structures including but not limited to the chest wall, spinal cord, heart, esophagus, aorta, kidneys, rectum, bowel, liver, and stomach within 5 cm of the GTV will be identified for the purpose of limiting incidental radiation to these structures.

In addition, prior to treatment delivery, a four-dimensional cone beam CT study will be performed on individual patients to assess respiration in these patients and to determine tumor targeting accuracy for those tumors that may be subject to respiratory motion such as those in the lung, abdomen, or liver. If tumor motion is greater than 5 mm, the planning target volume (PTV) will be expanded to account for respiration.

Within three weeks of the 1st cycle of checkpoint blockade, SBRT will be administered using image-guidance. An Vac-Lok (or equivalent immobilization device such as Alpha-Cradle) will be used to minimize movement of the chest, spine, and abdomen during treatment. During treatment, cone beam CT images of the patient's body site of interest will be obtained. Cone beam CT scan will be obtained immediately prior to treatment and will be repeated until the treatment shift, required to align the CT planning scan and the cone beam CT scan performed on the day of treatment cone beam CT, is within tolerance for the body site per standard clinical practice.

The patient will receive SBRT within 1-21 days of the start of Cycle#1 of CBI. Afterwards, the patient will continue to receive CBI as indicated and recommended by the treating medical oncologist. Patients will be evaluated for adverse events/toxicities during their treatment.

- 6.2.1 The dose limits for surrounding critical structures are as follows [Base in part from Stereotactic body radiation therapy: The report of AAPM Task Group 101, Med. Phys. 37(8), August 2010]:
  - Spinal Cord: maximal allowable total point dose is 2190cGy (7.3Gy/fx)
  - **Lung**: Combined mean lung dose < 400 cGy, V20<4%, and at least 1500cc < 1160 cGy
  - Heart: Volume of heart receiving 24 Gy should be <15cc
  - **Esophagus**: 50% of the esophagus volume should be kept under 1000 cGy and no single point dose in the esophagus should exceed 2700 cGy.
  - **Brachial Plexus**: maximal allowable point dose is 2400 cGy
  - Liver: Approx 2/3 of liver or at least 700cc < 1920c Gy
  - **Kidneys:** 2/3 volume of each kidney <1060 cGy.
  - Small Bowel: <5% of bowel limited to <2000 cGy.

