# 1. PROTOCOL SYNOPSIS

TITLE	Randomized Phase II Study of Checkpoint Blockade Immunotherapy combined with Stereotactic Body Radiation Therapy in Advanced Metastatic Disease.
STUDY PHASE	Phase II
INDICATION	Patients who will receive CBI immunotherapy with at least 1 site of measurable metastatic disease which will not be irradiated.
PRIMARY OBJECTIVE	To determine whether SBRT combined with concurrent CBI improves the relative objective response rate (CR+PR) compared to CBI alone in patients with metastatic disease.
SECONDARY OBJECTIVES	
 
To assess the safety and toxicity of CBI used concurrently with SBRT delivered in 3 fractions in patients with metastatic disease
 
To determine the progression free survival, overall survival, and rate of stable disease greater than or equal to 6 months in patients after completion of SBRT in combination with CBI
 
To assess whether SBRT combined with concurrent CBI results in improvements in anti-tumor immune responses compared to CBI alone
 

HYPOTHESIS	Concurrent SBRT and CBI will increase the relative objective response (CR+PR) rate by at least 33% compared to CBI alone.
STUDY DESIGN	Patients who will receive CBI and have at least 1 site of measurable metastatic disease which will not be irradiated will be candidates for study. Patients will be randomized (1:1) to CBI combined with SBRT or CBI alone. SBRT at 9.5Gy x3 fractions will be delivered within 1-21 days of the start of Cycle #1 of CBI. The first six patients will be treated and observed for toxicity in the safety run-in phase for 30 days after radiation before continuing with further accrual. Radiation dose reduction is allowed if necessary to meet tissue constraints (6Gyx3 Minimum Dose). Response rates will be determined from the non-irradiated lesion/lesions and three blood draws will be obtained to analyze anti-tumor immune responses.
SAMPLE SIZE BY TREATMENT GROUP	73 patients per group (146 patients total)

SUMMARY OF SUBJECT ELIGIBILITY CRITERIA	
 
At least 1 site of measurable metastatic disease which will not be irradiated.
 
Plan to treat patient with CBI
 
Age ≥3 years.
 
Lansky scale score of ≥70 (ages ≥ 3 or < 16 years)         OR         Karnofsky scale score of ≥70 (ages ≥ 16 or < 18 years)         OR         ECOG performance status ≤ 2 (18 years or older).
 
Histologic confirmation of malignancy (primary or metastatic tumor).
 

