#### 8.3) Dose Modification for SBRT:

Dose modifications to SBRT due to safety or toxicity concerns will be performed by the treating radiation oncologist as clinically indicated. This includes dose reduction below 9.5Gy x3 fractions in order to meet tolerances listed above for critical normal structures when deemed necessary by the treating radiation oncologist. The minimum dose of SBRT delivered will be 6Gy x3 fractions.

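### The small-bowel dose limit in section 6.2.1 is mis-worded: read literally it caps the volume of bowel that is spared, so it cannot serve as a tolerance

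*Combined protocol and SAP*

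**What the plan says.** Section 6.2.1 lists dose limits for eight normal structures and bases them in part on a published task-group report. The last line is "Small Bowel: <5% of bowel limited to <2000 cGy". Two other lines show the forms used elsewhere in the list: for the heart, "Volume of heart receiving 24 Gy should be <15cc"; for the kidneys, "2/3 volume of each kidney <1060 cGy".

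The limits have a stated use. Section 6.2 explains that nearby normal structures, bowel among them, are identified so that stray dose to them can be held down. The synopsis adds: "Radiation dose reduction is allowed if necessary to meet tissue constraints (6Gyx3 Minimum Dose". Section 8.3 repeats the rule: "This includes dose reduction below 9.5Gy x3 fractions in order to meet tolerances listed above for critical normal structures", with the floor "The minimum dose of SBRT delivered will be 6Gy x3 fractions". No other section restates or corrects the small-bowel line.

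**The concern.** A dose-volume limit can be written in two sound ways. It can cap the volume that receives a high dose, or it can require that a sufficient volume stay below a dose. The small-bowel line takes its volume term from the first form (a small percentage with a less-than sign) and its dose term from the second (a dose with a less-than sign). Joined together, they cap the volume that is protected.

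At stake is the usefulness of a stated safety threshold in the SBRT arm. The choice between 9.5 Gy x 3 and a lower dose is meant to depend on whether the listed limits are met. A planner, physicist or auditor who checks a plan against this line as printed gets the wrong answer for any plan that spares the bowel.

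**Working it through.** **Inputs.** From 6.2.1: 5% of bowel and 2000 cGy. From 8.3: full dose 9.5 Gy x 3 = 28.5 Gy = 2850 cGy; minimum dose 6 Gy x 3 = 18 Gy = 1800 cGy.

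**Step 1: compare the lines of 6.2.1.**
- Cap on the high-dose volume: heart, and the V20 term (taken in its usual sense) of the lung line, "Combined mean lung dose < 400 cGy, V20<4%, and at least 1500cc < 1160 cGy".
- Required volume below a dose: kidneys, liver, half of the esophagus, and the absolute-volume term for lung.
- Point maximum: spinal cord, brachial plexus, and the second part of the esophagus line.
- Cap on the volume below a dose: small bowel only.

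**Step 2: write the two rules.** Let v be the fraction of small bowel receiving 2000 cGy or more, so 1 - v is the fraction below 2000 cGy.
- As printed: pass if 1 - v < 0.05, that is, v > 0.95.
- Intended direction: pass if v < 0.05.

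| v (at or above 2000 cGy) | 1 - v (below 2000 cGy) | As printed | Intended |
|---|---|---|---|
| 0% | 100% | fail | pass |
| 1% | 99% | fail | pass |
| 4.9% | 95.1% | fail | pass |
| 5% | 95% | fail | fail |
| 50% | 50% | fail | fail |
| 95% | 5% | fail | fail |
| 95.1% | 4.9% | pass | fail |
| 100% | 0% | pass | fail |

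No v can be both above 0.95 and below 0.05, so no plan passes both rules. The verdicts are opposite at the two ends, and both rules reject everything from 5% to 95%.

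**Step 3: apply the dose-reduction rule.** Lowering the dose can only lower v or leave it unchanged, so it cannot bring a plan closer to the printed rule. Section 6.2 says "The dose will be prescribed to the minimal isodose line that completely covers the GTV plus a 5 mm margin", so bowel outside that line receives less than the prescribed dose. At the floor the prescribed dose is 1800 cGy, which is below 2000 cGy. If all the bowel lies outside the line, v = 0: the plan passes the intended rule and fails the printed one. The remedy in 8.3 therefore works for the intended limit and against the printed limit.

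**Step 4: test for a stray sign.** Suppose the first less-than sign is an accident.
- Read as a cap on the dose to the hottest 5% of bowel, the line requires v < 0.05, which is the intended rule.
- Read on the pattern of the kidney line, it would ask only that 5% of bowel stay below 2000 cGy, that is, 1 - v of at least 0.05, or v up to 0.95. That is hardly a limit at all and is implausible as intent.

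Context points to the first of these, but the printed characters alone do not settle it.

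**The case against.** The strongest reply is that the slip exposes itself. The line stands under a heading about dose limits for critical structures, and the literal rule would reject nearly every real plan, including any whose target is far from bowel. It could not be applied for long without someone noticing. Under 5.1.1 a radiation oncologist judges whether a lesion can be treated, 8.3 leaves dose changes to the treating radiation oncologist, and 6.2.1 attaches no consequence to a missed limit. This largely stands, and it is why severity is low. It does not rescue the text, because 8.3 points to these listed tolerances as the criterion and a criterion should be checkable as written.

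A second reply is that the fault rests on one or two comparison signs, which may have been altered when the document was converted; signs are visibly garbled in the laboratory criteria of 5.1.7. This cannot be wholly excluded. Against it, the other signs in 6.2.1 read sensibly.

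A third is that the correct values cannot be known without the cited report. That stands for the 5% and the 2000 cGy. It does not affect the direction of the limit, which the neighbouring lines and the stated purpose establish.

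A reader might go further and infer that the protocol steers planners towards irradiating bowel, or that patients will receive unsafe bowel dose. The documents do not support that. Section 6.2 states the opposite purpose, clinical judgement governs the dose, and nothing shows that anyone would apply the literal rule.

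**Conclusion.** The small-bowel limit is wrong as written and cannot be used as a pass/fail tolerance for the dose reduction described in the synopsis and 8.3. It is one line of eight. The conclusion on direction rests on the rest of 6.2.1 and the purpose given in 6.2. It assumes that the signs in the source file are as printed, and it takes the 5% and 2000 cGy as given, without verifying either.

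Practical severity is low, since the intent would probably be inferred by the people using the list. The number of patients with a target near bowel is not given, so no patient-level effect can be stated. It would also be a mistake to read this as a threat to the trial's result: no endpoint definition, sample-size input or planned analysis uses the limit.

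**What to change.** Restate the line as: *<5% of small bowel may receive >=2000 cGy*. Before doing so, the investigators should confirm the 5%, the 2000 cGy and the printed signs against the source they used.

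The cost is one line of wording, submitted as a protocol amendment for IRB approval under 14.1. It needs no extra patients, scans or visits, and nothing in section 15 has to change.
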